### 6.4 Definition of Dose-Limiting Toxicity

Dose limiting toxicity will be defined as any event which meets the criteria below and occurs within the 1st cycle of therapy (21 days).

The following drug-related adverse events will qualify as DLT if considered drug-related:

- Non-hematologic toxicity ≥ Grade 3 (CTCAE v4) **except:** transient electrolyte abnormality, alopecia, sub-optimally treated nausea, vomiting or diarrhea, and isolated elevation of gamma glutamyl transpeptidase. In particular,
  - Gastrointestinal toxicity (e.g. nausea, vomiting, diarrhoea, abdominal pain) or hypertension ≥ CTCAE Grade 3 despite optimal supportive care/ intervention.
  - Nintedanib (BIBF1120) related liver toxicity except GGT\*\*\* as specified below:
    - AST/ALT > 5x ULN\* independent of bilirubin
    - AST/ALT > 2.5 x ULN\*\* **together with** total bilirubin > 1.5 ULN\*\*

\* corresponding to CTCAE Grade 3 toxicity

\*\* corresponding to CTCAE Grade 2 toxicity

\*\*\* An isolated GGT elevation with no corresponding ALT/AST increase will not be considered as DLT.

- Hematological toxicity
  - CTCAE Grade 4 neutropenia that is uncomplicated (not associated with fever  $\geq 38.5^{\circ}\text{C}$ ) only if continuing for  $> 7$  days
  - CTCAE Grade 4 febrile neutropenia of any duration if associated with fever  $\geq 38.5^{\circ}\text{C}$
  - Platelet decrease to CTCAE Grade 4, or decrease to CTCAE Grade 3 associated with bleeding or requiring transfusions
- Inability to resume nintedanib (BIBF1120) dosing within 14 days of stopping due to treatment related toxicity
- In case adverse events with CTCAE Grade 3/4 were not judged as DLT from a clinical point of view, the Principle Investigator will obtain a confirmation from the individual investigator regarding the appropriateness of the judgment

Dose escalation will proceed within each cohort according to the scheme in **Table 3**.

Participants who do not have a DLT and who do not complete a full cycle of treatment (at least 75% of the prescribed dose of both nintedanib and capecitabine) will be replaced in the study.

Management and dose modifications associated with the above AEs are outlined in **Section 6.5** and **Section 6.5.2**.

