## **6.5 Dose Modifications**

### **6.5.1 Treatment Delay**

Treatment with both nintedanib (BIBF1120) and capecitabine must be interrupted in case any of the criteria listed in **Table 4** is fulfilled.

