**Table 4 Criteria to Interrupt Nintedanib and capecitabine due to an Adverse Event**

| If one criterion is met, nintedanib (BIBF1120) + capecitabine is to be interrupted   |
|---|
| 
 
• Nausea of CTCAE grade <math>\geq 3</math> despite optimal supportive care
 
• Vomiting of CTCAE grade <math>\geq 2</math> despite optimal supportive care
 
• Diarrhoea of CTCAE grade <math>\geq 2</math> for more than 7 consecutive days despite optimal supportive care
 
• AST and/or ALT <math>> 3 \times</math> ULN conjunction with bilirubin of <math>> 1.5 \times</math> ULN
 
• AST and/or ALT of CTCAE grade <math>> 5 \times</math> ULN
 
• Other non-hematological adverse event of CTCAE grade <math>\geq 3</math> considered drug-related*
 
• Neutropenia and fever <math>> 38.5^{\circ}\text{C}</math>
 
• Neutropenia CTCAE grade 4 for more than 7 days without fever
 
• Platelets <math>< 50,000 /\text{mm}^3</math> with clinically relevant bleeding
 
 |

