**Table 9 Recommended Dose Adjustments for Nintedanib (BIBF1120) and Capecitabine**

| CTCAE (v4.0) Adverse Reactions   | Dose Adjustment  |
|--|--|
| Diarrhea ≥ grade 2 for more than 7 consecutive days despite optimal antidiarrheal treatment
OR
Diarrhea ≥ grade 3 despite optimal antidiarrheal treatment | 1st episode 
 
• Reduce 1 dose level
 
         |
| Vomiting ≥ grade 2
AND/OR
Nausea ≥ grade 3 despite optimal anti-emetic treatment  | 2nd episode 
 
• Reduce 1 further dose level
 
 |

|   |  |
|---|--|
| 
AST and/or ALT elevations > 3 X ULN in conjunction with bilirubin of > 1.5 X ULN
 
OR
 
AST and/or ALT elevations of > 5 X ULN
 | 
3rd episode
 
 
• Stop treatment
 
 |
|---|--|

Management of all other AEs:

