### **10.2 Adverse Events of Special Interests (AESI)**

The following events are considered as Protocol-specified events of special interests:

- **Any gastrointestinal and non-gastrointestinal perforation, leakage, fistula formation, or abscess.**

In such cases the following additional information will need to be collected, documented in the respective comment field of the CRF page and the respective narratives of the SAE, and be forwarded to Boehringer Ingelheim:

- Location of perforation, leakage, fistula, abscess
- Location/extent of abdominal tumor manifestations
- Imaging & reports (CT, ultrasound, endoscopy, pathology, etc.)
- Prior surgery (location, wound healing complications)
- Concomitant diseases with GI involvement (e.g., M Crohn, vasculitis, tuberculosis, diverticulitis)

- Thromboembolic events (or predisposition)
- **Drug-induced liver injury.**

Drug-induced liver injury is under constant surveillance by sponsors and regulators and is considered a protocol-specified adverse event of special interest (AESI). Timely detection, evaluation, and follow-up of laboratory alterations of selected liver laboratory parameters to distinguish an effect of the investigational drug from other causes are important for patient safety and for the medical and scientific interpretation of the finding.

The following are considered as protocol-specified AESI:

- An elevation of ALT and / or AST > 5x ULN without bilirubin elevation measured in the same blood draw sample
- An elevation of AST and/or ALT > 2.5 fold ULN combined with an elevation of bilirubin to > 1.5 fold ULN measured in the same blood draw sample

Patients showing the above laboratory abnormalities need to be followed up until the protocol specific retreatment criteria have been met and according to **Appendix C** [Boehringer Ingelheim: *Procedures for the follow-up of drug-induced liver injury (DILI)*].

Protocol-specified AESI are to be reported to Boehringer Ingelheim an expedited manner similar to Serious Adverse Events (**Section 10.4**), even if they do not meet any of the seriousness criteria.

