## Definition

The following changes in the laboratory values are considered to be a protocol-specific significant adverse event for all patients with normal values for ALT/AST at baseline:

- an elevation of ALT and / or AST > 5x ULN without bilirubin elevation measured in the same blood draw sample
- an elevation of AST and/or ALT >2.5 fold ULN combined with an elevation of bilirubin to >1.5 fold ULN measured in the same blood draw sample

These definitions are in line with the current dose reduction recommendations as outlined in all study protocols for BIBF 1120.

Patients showing these laboratory abnormalities need to be followed up until the protocol specific retreatment criteria have been met.

For patients with elevated ALT/AST values at baseline special considerations apply, if they are eligible for inclusion into the trial, e.g. if liver metastasis are present and do not qualify as exclusion criterion. For those special cases the BI contact person should be involved.

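### The combined liver rows of Tables 4 and 9 start at AST/ALT above 3x ULN, but 6.4, 10.2 and Appendix C start at above 2.5x, so no rule requires a dose reduction after a first event in between

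*Combined protocol and SAP*

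**What the plan says.** Three places define the combined liver event at the lower threshold:

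- Section 6.4 counts nintedanib-related "AST/ALT > 2.5 x ULN" together with total bilirubin above 1.5x ULN as a DLT if it occurs in cycle 1. A footnote there equates both limits with CTCAE grade 2. The section then says "Management and dose modifications associated with the above AEs are outlined in" Sections 6.5 and 6.5.2.
- Section 10.2 lists as an AESI "An elevation of AST and/or ALT > 2.5 fold ULN combined with an elevation of bilirubin to > 1.5 fold ULN" in the same blood sample.
- Appendix C (Definition) uses the same limits. Its changes "are considered to be a protocol-specific significant adverse event for all patients with normal values for ALT/AST at baseline". It adds: "These definitions are in line with the current dose reduction recommendations as outlined in all study protocols for BIBF 1120".

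The dosing tables use a higher one:

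- Under 6.5.1 both drugs "must be interrupted in case any of the criteria listed in" Table 4. Its combined liver row is AST and/or ALT above 3x "ULN conjunction with bilirubin of" more than 1.5x ULN.
- Table 9 applies a one-level reduction at the first episode, a further level at the second and a stop at the third. Its combined liver row is AST and/or ALT above "3 X ULN in conjunction with bilirubin of" more than 1.5x ULN.

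**The concern.** Section 6.4 sends the reader to 6.5 for what to do after a DLT. For one of the DLTs it defines, neither liver row there matches. Appendix C claims agreement with the dose reduction rules, and for this protocol that claim is incorrect. The other liver limit, AST/ALT above 5x ULN, is the same in all five places, and no reason is given for 3x. That looks more like a number that was not harmonised than a deliberate choice.

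At stake is the restart dose. Liver enzyme elevation was the most common DLT in early nintedanib trials (1.4) and was dose-dependent (1.6.1). A patient whose event would count as dose-limiting in cycle 1 may go back to 200 mg bid. The two sites could also treat the same event differently.

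**Working it through.** No sample size or test statistic is involved. The check is a comparison of thresholds, one traced example and the size of the dose step.

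**1. Thresholds side by side**

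| Place | AST/ALT (x ULN) | Bilirubin (x ULN) | Consequence |
|---|---|---|---|
| 6.4 | >2.5 | >1.5 | DLT (cycle 1, nintedanib-related) |
| 10.2 | >2.5 | >1.5 | AESI, expedited report |
| Appendix C | >2.5 | >1.5 | Significant event (normal baseline ALT/AST) |
| Table 4 | >3 | >1.5 | Interrupt both drugs |
| Table 9 | >3 | >1.5 | Reduce one level |

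The uncovered band is AST/ALT above 2.5x and up to 3x ULN with bilirubin above 1.5x ULN.

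**2. Example: AST 2.7x, bilirubin 1.8x, normal baseline, nintedanib-related, cycle 1, first event**

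- 6.4, 10.2 and Appendix C: met.
- Table 4: combined row not met (2.7 is below 3); above-5x row not met; the row for other drug-related non-hematological events needs grade 3 or higher, and 6.4 labels these limits grade 2.
- Table 9: neither liver row met.
- Table 10, grade 2, first occurrence: hold until grade 1 or lower, then restart at the unchanged dose. A second and a third occurrence each cost one level; a fourth ends treatment. Whether Table 10 applies is not certain: it covers other adverse events, and 6.5.3 lists liver enzyme elevations among the specific ones.
- 6.5.2: interruption is the first measure, and a lower dose on restart is allowed, not required.

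Result: no rule requires a reduction.

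**3. What still protects the patient**

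- 6.3 requires bilirubin at or below ULN before a new cycle. In Phase II all scheduled on-treatment chemistry falls on Day 1 (Table 12), so an event found there delays the cycle.
- Table 5 requires bilirubin at or below ULN before restart after an interruption for toxicity.
- A delay of more than two weeks generally ends therapy, with an exception agreed for clinical benefit (list after Table 10).
- A drug-related event of grade 3 or higher meets the Table 4 row for other events. The band of concern is therefore limited to bilirubin below grade 3. Even at grade 3, Table 10 lowers the dose only where indicated.
- 1.8.1 and 6.6.1 speak of interruption for relevant liver toxicity, without a threshold.

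These rules decide whether and when treatment restarts. None fixes a lower dose after a first event in the band.

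**4. Size of the dose step (Tables 7 and 8)**

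- Nintedanib: 2 x 200 = 400 mg/day against 2 x 150 = 300 mg/day; (400 - 300)/400 = 25%.
- Capecitabine: 2000 against 1500 mg/m2/day; (2000 - 1500)/2000 = 25%.

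**5. Frequency**

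The documents give no rate; 1.6.2 says bilirubin rose along with the enzymes in only a small number of cases. For illustration, assume that n = 15 to 30 of the up to 30 additional Phase II patients have normal baseline ALT/AST, and that a share r has such an event. Expected number = n x r; chance of at least one = 1 - (1 - r)^n.

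| r (assumed) | Expected, n = 15 / 30 | At least one, n = 15 / 30 |
|---|---|---|
| 1% | 0.15 / 0.3 | 14% / 26% |
| 3% | 0.45 / 0.9 | 37% / 60% |
| 5% | 0.75 / 1.5 | 54% / 79% |

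Both inputs are assumptions, so the table shows scale only.

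**The case against.** The best defence is that the scheme is graded: reduce at once above 3x, reduce on recurrence below it. If Table 10 applies, it gives a definite hold, also mid-cycle, and a definite restart dose. AESI and Appendix C thresholds trigger reporting and follow-up, and a reporting threshold may properly be lower than one for a permanent dose cut. DLT status served dose escalation, which ended when dose level 2 was chosen. Most liver enzyme cases were reported at doses above this trial's: predominantly above 200 mg bid (1.4), mostly at 250 mg and above (1.6.1).

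Much of this stands and keeps the point small. It does not explain why 6.4 refers this DLT to rules whose liver rows leave it out, or why Appendix C states an agreement that does not exist.

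Two stronger readings are tempting, and the documents support neither. A reader might infer that events in the band go unmanaged; the holds and recovery rules above show otherwise. A reader might also cite the Appendix C introduction, which links raised transaminases with raised bilirubin to poor outcome. That pattern is aminotransferase at least 3x with bilirubin at least 2x ULN, not otherwise explained. Apart from a value of exactly 3x, the band lies below it, so that text is no argument for 2.5x.

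**Conclusion.** The inconsistency is real. For a first event with AST/ALT above 2.5x and up to 3x ULN and bilirubin above 1.5x ULN but below grade 3, no rule requires a dose reduction. On the reading that Table 10 applies, treatment restarts at full dose. The consequence is a 25% difference in the restart dose of each drug, in a narrow band of unknown frequency. This is a minor safety harmonisation; it does not touch the efficacy analysis. The conclusion rests on the grade 2 label in 6.4 and on reading Table 9's three steps as one sequence for all the reactions listed there.

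**What to change.** In the combined liver row of Tables 4 and 9, change the AST/ALT limit from above 3x to above 2.5x ULN, still with bilirubin above 1.5x ULN, for patients with normal ALT/AST at baseline. This is the group to which Appendix C limits its definition. For patients who enter with raised values (5.1 allows up to 1.5x ULN, or 2.5x with liver metastases), keep above 3x or use the case-by-case route in Appendix C. No other threshold needs to change.

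The cost is one number and one baseline qualifier in each of two tables, by amendment. No tests are added: Appendix C already asks for repeat liver tests within 48 hours and at least weekly follow-up. The downside is that a few patients (0.15 to 1.5 under the assumed rates) would lose 25% of the dose of both drugs. That cut is permanent (note to Table 8) and uses one of the two reductions allowed before a patient leaves protocol therapy. The row carries no drug-related qualifier, so a rise from liver progression or biliary obstruction would count, as it already does above 3x.

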## **6.5 Dose Modifications**

### **6.5.1 Treatment Delay**

Treatment with both nintedanib (BIBF1120) and capecitabine must be interrupted in case any of the criteria listed in **Table 4** is fulfilled.

**Table 4 Criteria to Interrupt Nintedanib and capecitabine due to an Adverse Event**

| If one criterion is met, nintedanib (BIBF1120) + capecitabine is to be interrupted   |
|---|
| 
 
• Nausea of CTCAE grade <math>\geq 3</math> despite optimal supportive care
 
• Vomiting of CTCAE grade <math>\geq 2</math> despite optimal supportive care
 
• Diarrhoea of CTCAE grade <math>\geq 2</math> for more than 7 consecutive days despite optimal supportive care
 
• AST and/or ALT <math>> 3 \times</math> ULN conjunction with bilirubin of <math>> 1.5 \times</math> ULN
 
• AST and/or ALT of CTCAE grade <math>> 5 \times</math> ULN
 
• Other non-hematological adverse event of CTCAE grade <math>\geq 3</math> considered drug-related*
 
• Neutropenia and fever <math>> 38.5^{\circ}\text{C}</math>
 
• Neutropenia CTCAE grade 4 for more than 7 days without fever
 
• Platelets <math>< 50,000 /\text{mm}^3</math> with clinically relevant bleeding
 
 |

**\*Excluding palmar-plantar erythrodysesthesia or other AE which is attributed to capecitabine alone (see Table 6).**

#### **Criteria for reinitiating therapy**

Criteria for reinitiating therapy: After therapy is stopped for toxicity, a patient is eligible to restart nintedanib (BIBF1120) and capecitabine if all the criteria listed in **Table 5** are met.

Capecitabine should only be restarted if the patient still falls within days 1 - 14 of the cycle. It should not be reinitiated during the scheduled 7 days off. If criteria to reinitiate therapy fall within the scheduled 7 day off period, nintedanib may be reinitiated as a single agent to complete that cycle.

If a patient has to interrupt intake of nintedanib (BIBF1120) + capecitabine due to an adverse event for more than 14 days, the decision to restart therapy needs to be discussed and agreed upon between the investigator and the sponsor.

**Table 5 Criteria to Restart Nintedanib and Capecitabine after Interruption**

| All criteria have to be met in order to restart nintedanib (BIBF1120) + capecitabine  |
|--|
| 
 
• Nausea CTCAE grade <math>\leq 2</math>
 
• Vomiting CTCAE grade <math>\leq 1</math>
 
• Diarrhea CTCAE grade <math>< 2</math>
 
• AST and ALT CTCAE grade <math>< 5 \times</math> ULN and bilirubin <math>\leq 1 \times</math> ULN
 
• No other non-hematological adverse event grade CTCAE <math>\geq 3</math> which is considered drug-related
 
• Absolute neutrophil count of <math>\geq 1000 / \text{mm}^3</math>, without fever
 
• Platelets <math>> 75,000 / \text{mm}^3</math>
 
 |

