**Table 10 Management of Additional Adverse Events for Either Drug**

| Grade of Event   | During a Course of Therapy   | Dose Adjustment for Next Cycle   |
|--|--|--|
| ≤ Grade 1  | No change in dose.   | Resume at same dose level  |
| Grade 2
1 st occurrence | Hold until ≤ Grade 1   | Resume at same dose level.   |
| Grade 2
2 nd occurrence | Hold until ≤ Grade 1   | Resume at 1 dose level lower   |
| Grade 2
3 rd occurrence | Hold until ≤ Grade 1   | Resume at 1 dose level lower   |
| Grade 2
4 th occurrence | Hold until ≤ Grade 1   | Permanently discontinue  |
| Grade 3   | Hold until < Grade 2   | Resume at 1 dose level lower, if indicated   |
| Grade 4   | Discontinue permanently or, if physician deems it to be in the patient's best interest to continue, interrupt until resolved to grade 0-1. | Permanently discontinue OR
Reduce capecitabine by 50% AND
Reduce nintedanib 1 dose level |

1 Excludes sub-optimally treated grade 2 diarrhea/ nausea and hypertension. At the investigator's discretion, dose reduction of capecitabine may be pursued after the first occurrence of grade 2 Palmoplantar erythrodysesthesia.

2 Participants requiring a delay of > 2 weeks should go off protocol therapy.

3 Participants requiring > 2 dose reductions should go off protocol therapy.

Recommended management for nausea and vomiting: antiemetics.

Recommended management for diarrhea: Loperamide antidiarrheal therapy. Dosage schedule: 4 mg at first onset, followed by 2 mg with each loose motion until diarrhea-free for 12 hours (maximum dosage: 16 mg / 24 hours) Adjunct antidiarrheal therapy is permitted and should be recorded when used.

Of note, in many cases, it will be difficult to firmly establish one of the agents as being causative of the adverse event (i.e. fatigue, nausea or diarrhea). As suggested above, in these instances, temporary cessation and/or dose reductions of both nintedanib and capecitabine are to be carried out. In the circumstance that an adverse event, which is not otherwise described herein, is felt to be clearly attributed to one of the two agents, but not the other, the putative inciting agent should be held, with dose modification of that agent only, as appropriate.

Patients should PERMANENTLY discontinue treatment in the event of:

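### After a drug-related Grade 3 non-hematological event, Table 5 permits a mid-cycle restart at Grade 2 but Table 10 holds treatment until Grade 1, and nothing says which prevails

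*Combined protocol and SAP*

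**What the plan says.** The point concerns drug-related Grade 3 non-hematological events that Table 9 does not cover (Table 9 handles diarrhea, nausea, vomiting and liver enzymes). Hand-foot syndrome and events attributed to capecitabine alone are also outside it, because Table 4 sends them to Table 6.

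- **Interruption.** Table 4 stops both drugs for an "Other non-hematological adverse event of CTCAE grade" 3 or higher that is considered drug-related.
- **Restart, Section 6.5.1.** The rule reads "After therapy is stopped for toxicity, a patient is eligible to restart nintedanib (BIBF1120) and capecitabine if all the criteria listed in", and the list it points to is Table 5. The relevant Table 5 item begins "No other non-hematological adverse event grade CTCAE" and bars only drug-related events of grade 3 or higher.
- **Restart within the cycle.** "Capecitabine should only be restarted if the patient still falls within days 1 - 14 of the cycle". In the off week, nintedanib may restart alone.
- **Table 10, Grade 3 row.** Under the column headed "During a Course of Therapy", the instruction is "Hold until < Grade 2". Dose instructions for the next cycle have their own column.
- **Neighbouring rules.** Section 6.3 requires such toxicity to be at grade 1 or baseline before a new cycle. Section 6.5.1.1 requires grade 1 or less before capecitabine is restarted after a capecitabine-only event.
- **Long interruptions.** Section 6.5.1 says that if intake stops "for more than 14 days, the decision to restart therapy needs to be discussed and agreed upon between the investigator and the sponsor". Table 10 footnote 2 takes the patient off protocol therapy and states no exception. The permanent-discontinuation list after Table 10 allows an exception for clinical benefit, with prior agreement of the principal investigator.

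**The concern.** A site that works from Table 5 may re-expose a patient to nintedanib, and early in the cycle to capecitabine as well, while a Grade 2 drug-related toxicity persists. A site that works from Table 10 would still be holding both drugs. Two sites enroll, so the same event could be handled in two ways. That affects patient safety first, and then the consistency of dose exposure and toxicity data in a 36-patient single-arm phase II.

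The 14-day wording matters because holding to Grade 1 lengthens some holds. More of them can then pass 14 days, where the text decides whether the patient stays on therapy.

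**Working it through.** The plan states no figure on this point, so the check is a comparison of texts followed by an illustration of timing.

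**Step 1: one event through each rule.** Take a drug-related Grade 3 event within scope that has improved to Grade 2.

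| Rule | When it applies | Grade needed | Result at Grade 2 |
|---|---|---|---|
| Table 5 with Section 6.5.1 | restart after interruption, including mid-cycle | below 3 | restart permitted |
| Table 10, Grade 3 row | within the cycle | below 2 | keep holding |
| Section 6.3 | before a new cycle | 1 or baseline | not yet (unless baseline) |
| Section 6.5.1.1 (capecitabine-only events) | restart of capecitabine | 1 or less | not yet |

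Three of the four rules use grade 1. Section 6.3 agrees with Table 10 except for its baseline allowance, so the mismatch is confined to restarts within a cycle.

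**Step 2: when in a 21-day cycle the mismatch can arise.** Let onset fall on cycle day d, counted as hold day 1, so hold day h is cycle day d + h − 1. Suppose Grade 2 is reached on hold day g. The values of g are assumptions; the documents give none.

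- Both drugs could restart if d + g − 1 ≤ 14, which is 15 − g onset days.
- Nintedanib alone could restart if 15 ≤ d + g − 1 ≤ 21, which is 7 onset days.
- No restart in the same cycle if d + g − 1 > 21, which is g − 1 onset days. Section 6.3 then governs.

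| g | Both drugs | Nintedanib alone | No mismatch | Sum |
|---|---|---|---|---|
| 4 | 11 | 7 | 3 | 21 |
| 7 | 8 | 7 | 6 | 21 |
| 10 | 5 | 7 | 9 | 21 |
| 14 | 1 | 7 | 13 | 21 |

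**Step 3: doses in dispute for one assumed course.** Let Grade 2 be reached on hold day 10 and Grade 1 on hold day 16. The disputed days are hold days 10 to 15, or cycle days d + 9 to d + 14.

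- Nintedanib, two doses a day up to cycle day 21: 6 × 2 = 12 doses for onset on days 1 to 7, then 10, 8, 6, 4 and 2 for days 8 to 12, and 0 from day 13.
- Capecitabine, two doses a day up to cycle day 14: for onset on day 1, cycle days 10 to 14 give 5 × 2 = 10 doses. The count falls to 8, 6, 4 and 2 for days 2 to 5, and is 0 from day 6.

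In this course, Table 10 keeps treatment off through hold day 15, which is more than 14 days. Table 5 would have allowed a restart on day 10. The choice of table therefore also decides whether the 14-day rule is reached.

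**The case against.** **The tables can be reconciled.** Table 5 also says that all its items have to be met before restart, which reads as a set of necessary conditions. A site that holds to Grade 1 breaks neither table. This stands, and a reader who infers flatly opposite commands goes too far: Table 5 permits an early restart and does not require one. But the sentence introducing Table 5 makes meeting it enough for eligibility, and nothing says the stricter table wins.

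**The Table 10 Grade 2 rows add little.** They say "Hold until ≤ Grade 1", and a reader might infer that a patient restarted at Grade 2 breaches them too. Those rows are counted by occurrence, and a Grade 3 event on its way down is more naturally still the Grade 3 event. Footnote 1 also exempts hypertension from them. The conflict is one Table 5 item against one Table 10 row.

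**Practice limits the exposure.** After cycle 1, phase II schedules toxicity visits only on day 1 of each cycle, where Section 6.3 governs, so a mid-cycle restart would need unscheduled contact. Section 6.5.2 allows resumption at a reduced dose, and Appendix A provides weekly or bi-weekly calls on adverse events. These points stand as mitigation. They do not settle which table applies.

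**The 14-day texts are nearly one rule.** A reader might infer three unconnected rules. The discontinuation list does refer back to earlier text, footnote 2 can be read as its short form, and the sponsor is also the lead institution, so the approver may be the same in practice. What stands is narrower: the back-reference has no section number, and Section 6.5.1 lacks the clinical-benefit condition.

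**Conclusion.** The inconsistency is in the current text and should be corrected. For the events in scope, Table 5 permits a mid-cycle restart at Grade 2, Table 10 holds until Grade 1, and the neighbouring rules side with Table 10. Confidence in that single mismatch is high.

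Its size in patients is unknown because the documents give no rate for these events. The onset-day and dose counts rest on assumed recovery times and same-day regrading. They show only where the mismatch can arise, and 12 and 10 doses are the maxima for one invented course.

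A reader might infer that dose finding or the primary analysis is compromised. The documents do not support that: the recommended phase II dose was already fixed as of 1/29/16, and the hypothesis test, its error rates and the sample size do not depend on the restart grade. A reader might also infer that events blamed on both drugs are governed more loosely than capecitabine-only events. That is so only if Table 10 is disregarded.

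The 14-day point is secondary and concerns wording only.

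**What to change.** **Restart grade.**

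- Table 5: replace the item on other non-hematological events with *Any other drug-related non-hematological adverse event of grade 3 or higher has resolved to grade 1 or less (or baseline)*.
- Table 10, Grade 3 row: change the hold to *Hold until grade 1 or less (or baseline)*. Both tables then match Section 6.3. Adding the baseline allowance to Table 5 alone would leave a new mismatch for a patient with Grade 2 toxicity at baseline.
- If Grade 2 hypertension is acceptable for restart, name that exception in both tables.

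**Interruptions of more than 14 days.** Make the permanent-discontinuation list after Table 10 the single rule, and cite it in the last sentence of the restart text in Section 6.5.1 and in Table 10 footnote 2. The unnumbered back-reference in that list can then be deleted.

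**Cost.** These are wording edits, with no added patients, visits or scans. Some holds will be longer. Under Section 6.1 a cycle is not extended for missed doses and they are recorded as omitted, so in the illustration up to 12 nintedanib and 10 capecitabine doses would be lost instead of being given during Grade 2 toxicity.
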